Retrograde analysis of data of all patients presented to Aboul Reesh uveitis clinic taking biologics from January 2017- January 2020. In our hospital, the rationale for using biologics was a high frequency of sight-threatening, frequent recurrences of uveitis or intolerance to steroids or other immunosuppressive drugs, with severe adverse reactions.

Sample size:

It is expected to review 250 patients files of Aboul Reesh uveitis clinic to find all JIA patients with ocular inflammation treated with biologics.

Inclusion criteria

1. Both genders
2. Age up to 16 years
3. Diagnosed JIA according to rheumatological criteria with ocular affection
 - Any type of arthritis (oligoarticular, polyarticular, systemic onset, ocular JIA)
 - ANA positive or negative
4. Uncontrolled uveitis or frequent relapses

Exclusion criteria:

1. Patients without definitive diagnosis as JIA

2. JIA patients on biologics without ocular affection (for systemic control) or with uveitis controlled without the use of biologics
4. Patients without adequate duration for follow-up (less than 3 months) or lost follow up data
5. Patients without available data prior to the start biologics (to compare control of the uveitis)

Methodology

Data will be obtained from by retrospective analysis of all files of patients with JIA from the Abou El Reesh ophthalmology outpatient clinic.

The patients with ocular inflammation treated by biologics will be further analyzed.

The data analyzed will divided into pre and post biologic treatment:

In both we will document-

-Baseline BCVA (in logMar notation)

- Grading of ocular inflammation

(Anterior chamber and vitreous cells were graded as +0.5, +1, +2, +3 and +4 according to the guidelines of the Standardization of Uveitis Nomenclature Working Group)

- Number of relapses in one year

- Development of sight threatening complication

- Dose and frequency of systemic, regional and topical steroids

- Other interventions required

Treatment parameters to be analyzed include type, duration and dose of biologic agent used, time taken to reach inflammation control, adverse effects, and time taken to develop those adverse effects.

Improvement or worsening of activity of inflammation was assessed according to the Standardization of Uveitis Nomenclature Group's directions (2 step improvement or worsening of cells/flare)

Treatment was determined as efficacious if one of the following was fulfilled:

1. No relapses or decrease in the number of relapses

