2. Decrease in dose of topical or systemic steroids
3. Improvement of BCVA of at least two lines

Statistical analysis plan:

All data will be entered into Excel spreadsheets (Microsoft Corporation, Redmond, WA, USA). All statistical analyses will be performed using IBM SPSS version 22.0 software (IBM Corp., Armonk, NY, USA). Descriptive statistics will be summarized as the mean \pm standard deviation for numerical data, frequencies and percentages for categorical data. The ANOVA -test and Pearson moment correlation will be used to compare the means for the numerical data and to identify correlations between them. Chi-square test will be used to compare categorical data. P-values ≤ 0.05 will be considered statistically significant.

References

- 2) Qian Y, and Nisha R. (2010) Juvenile Idiopathic Arthritis Associated Uveitis. *Curr Opin Ophthalmol.* 21(6): 468–472. doi:10.1097/ICU.0b013e32833eab83

Retrospective Analysis of the Use of Biologics for Juvenile Idiopathic Arthritis Related Uveitis in Abou El Reesh Pediatric Hospital, Cairo University

First version, 1st march 2020

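### The pre/post biologic contrast is within-child, but the analysis plan names no paired test, assigns no test to any comparison and does not state whether the unit is child or eye

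*Combined protocol and SAP*

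**What the plan says.** The Methodology sets up the contrast: "The data analyzed will divided into pre and post biologic treatment". It then says "In both we will document" and lists BCVA in logMAR, inflammation grade, relapses in one year, sight-threatening complications, steroid use and other interventions. The Exclusion criteria remove "Patients without available data prior to the start biologics (to compare control of the uveitis"), so every analysed child should supply a pair. No separate control group is described.

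The Statistical analysis plan covers inference in two sentences: "The ANOVA -test and Pearson moment correlation will be used to compare the means for the numerical data" and to identify correlations, and "Chi-square test will be used to compare categorical data". Descriptive results are "frequencies and percentages for categorical data", with mean and standard deviation for numerical data. Significance is declared at P ≤ 0.05.

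Separately, the Methodology defines success per child: "Treatment was determined as efficacious if one of the following was fulfilled". The first criterion is "No relapses or decrease in the number of relapses"; the others are a lower steroid dose and a BCVA gain of two lines or more.

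**The concern.** On their ordinary reading, ANOVA and the chi-square test treat the groups compared as independent. Here the two groups would be the same children at two times. The variance of the change then depends on the correlation between a child's two values, and an unpaired test ignores it. The plan names none of the methods that use the pairing: paired t-test, repeated-measures ANOVA, signed-rank test, McNemar's test or a mixed model.

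At stake are the direct pre/post significance tests on BCVA, cell grade, steroid dose, relapses and binary outcomes. In a small series a conservative test can miss a real change. The unit of analysis adds a second problem: BCVA and cell grade are measured per eye, and the plan does not say how a child's two eyes enter the analysis. Because the mapping of tests to comparisons is open, two analysts following the plan could also obtain different p-values from the same data.

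**Working it through.** **Inputs.** From the documents: the paired design (Methodology, Exclusion criteria), the tests and the 0.05 level (Statistical analysis plan). Two-sided testing is assumed because sidedness is not stated. The 250 in the Sample size section is a count of files to review. The documents give no analysed number, SD, effect size or correlation, so there is no planned figure to reproduce and every value below is assumed.

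**1. One value per child per period: type I error.** With equal SD σ, n children and pre/post correlation r:

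- true variance of the mean change = 2σ²(1 − r)/n
- variance assumed by the unpaired test = 2σ²/n
- true type I error at nominal 5% = 2[1 − Φ(1.96/√(1 − r))]

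| r | 1.96/√(1 − r) | Type I error, formula | Simulated, n = 30 |
|---|---|---|---|
| −0.2 | 1.789 | 7.4% | 7.3% |
| 0 | 1.960 | 5.0% | 5.0% |
| 0.3 | 2.343 | 1.9% | 2.0% |
| 0.5 | 2.772 | 0.6% | 0.7% |
| 0.7 | 3.578 | 0.04% | 0.08% |

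The paired t-test stays at about 5% throughout (simulated 4.9–5.1%).

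**2. Power.** The paired t-test has noncentrality d√n/√(2(1 − r)), where d is the change in SD units. For d = 0.5, n = 30, r = 0.5 this is 0.5 × 5.477/1 = 2.74, giving 75% power. Paired / unpaired (two-group ANOVA), by simulation:

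| n, change | r = −0.2 | r = 0 | r = 0.3 | r = 0.5 | r = 0.7 |
|---|---|---|---|---|---|
| 20, 0.5 SD | 28/35% | 32/34% | 44/31% | 57/29% | 78/24% |
| 30, 0.5 SD | 40/48% | 46/48% | 61/47% | 75/47% | 93/47% |
| 50, 0.5 SD | 61/68% | 69/70% | 83/73% | 93/76% | 99/82% |
| 98, 0.5 SD | 88/92% | 93/94% | 98/96% | 100/98% | 100/100% |
| 30, 1 SD | 93/96% | 96/97% | 99/98% | 100/100% | 100/100% |

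The unpaired advantage at r = −0.2 comes with an inflated type I error (step 1). The row at 98 is 250 × 0.39 = 97.5, using the JIA share in the Background. It is only a rough figure.

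**3. Cell grade.** Six ordered levels (zero plus the five listed grades, assumed cut-points), n = 30, latent 0.5 SD shift, signed-rank / ANOVA power: 42/45% at r = 0, then 54/44%, 68/44% and 85/40% at r = 0.3, 0.5 and 0.7.

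**4. Binary outcome.** Fall from 60% to 35%, n = 30, full enumeration of the paired 2×2 table with within-child correlation φ:

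| φ | Mid-p McNemar | Asymptotic McNemar | Chi-square |
|---|---|---|---|
| 0 | 47% | 48% | 50% |
| 0.15 | 53% | 53% | 50% |
| 0.3 | 61% | 61% | 50% |
| 0.5 | 78% | 80% | 50% |

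Type I error over φ = 0 to 0.5: mid-p 3.7–4.7%, asymptotic 4.3–4.8%, chi-square falling from 5.2% to 0.6%. Exact McNemar is itself conservative (1.8–2.8%) and weaker than chi-square at φ = 0 and 0.15 (39% and 44% against 50%).

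**5. Both eyes pooled as independent units.** Under the unpaired test, the ratio of true to assumed variance is 1 + r(fellow eyes, same time) − r(same eye, pre/post) − r(cross-eye, pre/post).

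- Assumed 0.8, 0.3, 0.25: 1 + 0.8 − 0.3 − 0.25 = 1.25. Type I error = 2[1 − Φ(1.96/√1.25)] = 8.0%.
- All three at 0.5: ratio 0.5, type I error 0.6%.

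The direction therefore turns on whether the fellow-eye correlation exceeds the sum of the two pre/post correlations. Pairing by eye while ignoring the child does not cure this: with a correlation of 0.3/0.5/0.7 between the two eyes' changes, 2[1 − Φ(1.96/√(1 + ρ))] gives 8.6/11.0/13.3%.

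**The case against.** The strongest reply is that the Statistical analysis plan is generic and assigns no test to the pre/post contrast. Repeated-measures ANOVA is still ANOVA, McNemar's statistic is also referred to a chi-square distribution, and the Methodology lists variables that differ between children (type, dose and duration of biologic) for which the ordinary tests are suitable. This stands in part. A reader might infer that the plan commits to analysing paired data as independent; the text does not go that far. It establishes an omission: no paired method is named, and if the listed tests are meant only for comparisons between children, the pre/post contrast has no test at all.

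A reader might also infer that the tests are simply conservative, and so safe. That holds only for one value per child per period with a positive correlation. The unit is not stated, and step 5 shows the error can run the other way. Nor is a positive correlation given: including children for uncontrolled uveitis or frequent relapses may lower it.

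A third tempting inference is that the efficacy results are invalid. They are not. Each criterion, like the two-step change in inflammation, compares a child with their own earlier state, so the pairing is built in. These classifications suit the planned frequencies and percentages and can be compared across biologic types by chi-square.

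Finally, the loss may be negligible: about 1 point for a 1 SD change at n = 30, and at most 2 points at n = 98, for r = 0.3 to 0.7. That is correct, but 98 should not be read as a bound. The 39% comes from a separate unpublished cohort, and the Methodology describes the source as the files of JIA patients, which leaves unclear what the 250 files contain. The analysed series could be much smaller.

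**Conclusion.** The point holds as a gap that should be fixed. The plan does not say which test serves which comparison, names no paired test for a within-child contrast and does not state the unit of analysis. The omission is certain from the text; its consequence depends on how the tests are applied.

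If ordinary ANOVA or chi-square is used on one value per child per period, the standard errors and p-values are wrong unless the pre/post correlation is zero. For an assumed 30 children and 0.5 SD change, 14 to 46 points of power are lost at correlations of 0.3 to 0.7 (61 − 47 and 93 − 47). At a negative correlation the error reverses. With eyes pooled, type I error may be below or above 5% even when all the correlations are positive. These sizes rest wholly on assumed inputs and illustrate a range; they do not estimate this study's loss.

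**What to change.** State the unit of analysis and the test for each comparison.

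- **Unit:** the child for all pre/post tests. If both eyes are entered, use a mixed model or GEE clustered on the child.
- **BCVA (logMAR):** paired t-test on the child's mean of affected eyes, or on one pre-specified eye.
- **Cell grade:** Wilcoxon signed-rank on the worse eye or one pre-specified eye; ordinal grades should not be averaged.
- **Steroid dose:** Wilcoxon signed-rank.
- **Binary outcomes that can occur in both periods:** McNemar, asymptotic or mid-p (choose one in advance), with the outcome defined per child, for example present in either eye. A mean over two eyes cannot feed this test.
- **Relapses:** a per-child rate over the observed time in each period, by signed-rank on the rate difference or a count model with log observation time clustered on the child. The Methodology counts relapses over one year, but the Exclusion criteria remove only follow-up under 3 months, so pairing raw counts would not make them comparable.
- **Reporting:** each change with a 95% CI, and the per-child efficacy criteria as proportions with a 95% CI.
- **ANOVA, Pearson and chi-square:** keep for comparisons between different children, such as by biologic type.

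The cost is analysis wording. The listed outcomes stay the same; the relapse rates also need each child's observation time in each period, taken from the same files.

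### The SAP does not say which groups ANOVA and chi-square compare; if type of biologic is one of them, no adjustment for the pre-biologic value is planned, although agents were not randomised and every analysed child has that value.

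*Combined protocol and SAP*

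**What the plan says.** The Statistical analysis plan section gives one sentence to numerical data: ANOVA and "Pearson moment correlation will be used to compare the means for the numerical data and to identify correlations between them". It gives one to categorical data: "Chi-square test will be used to compare categorical data". The threshold follows: "P-values ≤ 0.05 will be considered statistically significant". The section names no groups, paired or repeated-measures form, covariate, regression or stratification.

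The Methodology section sets out one contrast: "The data analyzed will divided into pre and post biologic treatment". Acuity, inflammation grade, relapses, complications, steroid use and other interventions are to be documented in both periods. The same section then says: "Treatment parameters to be analyzed include type, duration and dose of biologic agent used, time taken to reach inflammation control", followed by adverse effects and their timing. No sentence says that types will be compared with each other.

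Item 5 of the exclusion criteria removes "Patients without available data prior to the start biologics (to compare control of the uveitis"). Every analysed child therefore has pre-biologic data. The study is retrospective. The population section gives reasons for using a biologic at all, but none for choosing one agent over another.

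**The concern.** Type is a categorical variable marked for analysis, and in their ordinary form ANOVA and chi-square compare independent groups. An analyst following the SAP could reasonably run them across agents and call a p-value of 0.05 or less significant.

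Clinicians chose the agents. The reasons given for starting a biologic (sight-threatening disease, frequent recurrence, drug intolerance) are different in kind and may go with different starting severity. If they are unevenly spread across agents, the agent given to the harder cases will look worse even when the agents work equally well. The value needed to correct for the measured part of that difference is already in the file, but no planned between-child test uses it. Leaving it out also keeps avoidable residual variance in what is likely to be a small sample.

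**Working it through.** **The plan's own figures.** The only count is 250 files to be screened. It is not a calculated sample size, so there is nothing to reproduce. If the 39% JIA share in the background applied to this clinic, 0.39 × 250 = 97.5, or about 98 files, would be JIA. The share on biologics, the number per agent, and all standard deviations and correlations are absent.

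**Inputs.** From the documents: the 0.05 threshold (taken as two-sided; the SAP does not say), unadjusted tests, and a pre value for each child. Assumed: two agents with n1 = 28 and n2 = 10; no true difference between them; pre and post values with SD 1 and correlation r; a baseline gap of d SD between the groups.

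**Formulas.**
- Post value alone: the spurious mean difference is r × d and the SD is 1.
- Change score: the mean difference has size (1 − r) × d and the SD is √(2 − 2r).
- Each standardised difference is multiplied by √(n1·n2/(n1 + n2)) = √(280/38) = 2.714 to give the noncentrality of a t-test on 36 df (critical value 2.028).
- ANCOVA on the pre value: the expected difference is r·d − r·d = 0, so the rejection rate should stay at 5%.

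Worked example, d = 0.8 and r = 0.5. Post value: 0.5 × 0.8 = 0.40, noncentrality 0.40 × 2.714 = 1.086, rejection 18.5%. Change score: 0.5 × 0.8/√1 = 0.40, hence also 18.5%.

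| d (SD) | r | Post value alone | Change score | ANCOVA |
|---|---|---|---|---|
| 0 | any | 5% | 5% | about 5% |
| 0.5 | 0.3 | 6.8% | 12.2% | about 5% |
| 0.5 | 0.5 | 10.1% | 10.1% | about 5% |
| 0.5 | 0.7 | 15.2% | 8.1% | about 5% |
| 0.8 | 0.3 | 9.7% | 24.0% | about 5% |
| 0.8 | 0.5 | 18.5% | 18.5% | about 5% |
| 0.8 | 0.7 | 31.6% | 13.0% | about 5% |
| 1.0 | 0.3 | 12.5% | 34.6% | about 5% |
| 1.0 | 0.5 | 26.2% | 26.2% | about 5% |
| 1.0 | 0.7 | 45.6% | 17.6% | about 5% |

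The ANCOVA column was simulated (40,000 studies per cell; 4.8% to 5.2%). The other columns are exact under normality.

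**Other group sizes.** In simulations with equal groups, d = 1.0 and r from 0.3 to 0.7, the post value alone rejects in 10% to 32% of studies at 10 children per agent, 15% to 58% at 20, and 26% to 87% at 40. More children make the error more frequent, not less.

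**Variance.** The covariate removes r² of the residual variance: 25% at r = 0.5 and 49% at r = 0.7.

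**Limit of the remedy.** Add an unmeasured group difference of 0.4 SD in the post value (again assumed) to the d = 0.8 case. ANCOVA then rejects in about 21% (r = 0.5) to 28% (r = 0.7) of studies.

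**The case against.** The strongest reply is that no between-agent comparison is planned. A frequency table of types would satisfy the Methodology wording, and the SAP does plan frequencies and percentages. The aim concerns biologics as a class, and the one stated contrast is before versus after, for which ANOVA may be intended. The efficacy criteria are themselves changes within a child (relapses, steroid dose, lines of acuity), so a test on them would already draw on the pre value.

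Most of this stands. A reader might infer that the plan compares agents on post values and attributes the difference to the agent; the documents say none of these things. A reader might also infer that later agents went to children in whom an earlier one had been inadequate. The only support is a guideline cited in the background, which does not describe local practice. So groups by agent may differ, not must. ANA status and arthritis type appear only in the inclusion criteria, so they cannot be called planned comparisons.

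Two parts do not dispose of the point. The SAP does not confine type to description, so the reader cannot tell which analysis is intended. Building the pre value into a change is also not the same as adjusting for it, as the change-score column shows.

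It is fair to add that the missing paired method for the before/after comparison bears more directly on the stated aim. That is a separate gap.

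**Conclusion.** The concern holds conditionally. The SAP leaves its contrasts unstated; if type of biologic is used as a grouping factor, the only named tests are unadjusted in a non-randomised cohort, while the main covariate is available for every child.

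With 28 and 10 children, equal agents and r of 0.5 to 0.7, false positives from the post value alone would be about 10% to 15% at a 0.5 SD gap, 18% to 32% at 0.8 SD and 26% to 46% at 1.0 SD. ANCOVA stays at about 5%. Change scores give 13% to 26% at gaps of 0.8 to 1.0 SD. With no gap, every method gives about 5%.

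Group sizes, gap and correlation are all assumptions, so the size in this study cannot be determined from the documents. The 5% for ANCOVA holds only when the baseline difference lies wholly in the measured covariate. It should not be read as showing that adjustment removes confounding by indication.

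**What to change.** 1. State which groups or periods each test compares, and say whether type of biologic is a grouping factor or only described.
2. For any between-agent comparison of an outcome that has a pre-biologic value, include the child's own pre value as a covariate: ANCOVA for BCVA, a count model for relapses, an ordinal model for cell grade. Where numbers allow, add an indicator for first versus later biologic.
3. Report outcomes with no pre value (such as time to control and adverse effects), and agents used in very few children, descriptively and without testing.
4. Label all between-agent results exploratory, give intervals, do not rank agents, and note that unmeasured confounding by indication remains.

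The cost is SAP wording, one or two degrees of freedom, and one extra field (previous biologic, yes or no) from the same files. With few children per agent the adjusted model may not be supportable; item 3 then applies.

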Full Protocol

**Retrospective Analysis of the Use of Biologics for Juvenile Idiopathic
Arthritis Related Uveitis in Abou El Reesh Pediatric Hospital, Cairo
University**

Background and introduction

Juvenile Idiopathic Arthritis (JIA) remains, globally, the most common systemic disorder associated with pediatric uveitis. It accounts for approximately 75% of cases of pediatric anterior uveitis (AU) and affects around 30% of ANA positive JIA patients (regardless their type of arthritis).¹ In a cohort study from the Cairo University Pediatric Hospital, JIA accounted for 39% of all cases of pediatric uveitis (unpublished data).

The uveitis, being asymptomatic, chronic and often severe, leads to complications in a large number of patients. Studies estimate that 28–67% of patients with JIA-associated uveitis develop ocular complications, with 12% developing poor visual outcome. The main causes of poor vision were cataract, band keratopathy and macular edema.²

The only means of improving long term effects of uveitis, is early and aggressive anti-inflammatory treatment.³

The main line of treatment of non-infectious causes of uveitis have been topical and systemic corticosteroids. However, it is well known that their prolonged use often leads to ocular and systemic complications, especially in the pediatric age group.⁴

In 2019, the American College of Rheumatology/Arthritis Foundation recommended that in severe active chronic AU or in the presence of sight-threatening complications, methotrexate (MTX) and a monoclonal antibody TNFi should be administered immediately. This is recommended over MTX as monotherapy. They also recommended that inadequate response to one monoclonal TNFi at standard JIA dose, the dose and or frequency should be increased rather than switching to another monoclonal antibody TNFi.⁵

Immunosuppressive drugs are used as steroid-sparing agents but are not free of complications. They increase the susceptibility of children to infection, may cause organ toxicity, reversible bone marrow suppression and may possibly lead to the development of malignancies.³

Thus, our study aims to analyze the use of biologics in our hospital (Abou el Reesh, Cairo University) for children with JIA in controlling their ocular inflammation, prevention of the development of sight threatening complications and if this outweighs their potential associated side effects.

Patients and methods

Population of study & disease condition

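### Chi-square is the only test named for categorical data, so its p-value may mislead if rare adverse effects are compared between groups of unequal size

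*Combined protocol and SAP*

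**What the plan says.** The Statistical analysis plan is one paragraph. For categorical variables it says "Chi-square test will be used to compare categorical data", and for the decision rule "P-values ≤ 0.05 will be considered statistically significant". It names no exact test, continuity correction, minimum expected count or paired test.

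The Sample size section gives a screening figure only: "It is expected to review 250 patients files of Aboul Reesh uveitis clinic to find all JIA patients with ocular inflammation treated with biologics". The Background reports for the same university's pediatric hospital that "JIA accounted for 39% of all cases of pediatric uveitis". Methodology then narrows the set: "The patients with ocular inflammation treated by biologics will be further analyzed". The Exclusion criteria remove further children, including "Patients without adequate duration for follow-up (less than 3 months) or lost follow up data", and those with no data from before the biologic was started. The number expected to remain is not given.

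Methodology lists the type of biologic and adverse effects among the treatment parameters to be analysed. It does not say that one will be tested against the other. The arthritis types ("Any type of arthritis (oligoarticular, polyarticular, systemic onset, ocular JIA") and ANA status appear only under Inclusion criteria. The comparison that the plan does lay out is before versus after biologic treatment in the same children.

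**The concern.** The chi-square p-value is a large-sample approximation that becomes unreliable when expected counts are small. The plan applies it to every categorical comparison, whatever the counts. The analysed group is some fraction of about 98 children, and agents or subtypes may be used unevenly, so a table of adverse effects by agent could have expected counts well under 5.

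The stated aim includes judging whether the benefit of biologics outweighs their side effects. A single adverse effect in a seldom-used agent could be labelled a significant difference under the plan's own rule when an exact test gives no such signal. If the test is left open until the data are seen, the choice between the two p-values could also be made after the fact.

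**Working it through.** There is no plan figure to reproduce: 250 is a count of files, with no power, effect size or formula behind it.

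**Inputs**
- Files: 250 (Sample size). JIA share: 39% (Background). 250 × 0.39 = 97.5, about 98 JIA files, if all the files are pediatric uveitis files and the share applies to them.
- Share on biologics: not stated. An assumed 10–50% of 98 gives about 10 to 49 children. Step 1 covers N = 10 to 98.
- Significance: p ≤ 0.05. Uncorrected Pearson chi-square is assumed, since no correction is named.
- Event rates: the Background gives 28–67% for ocular complications and 12% for poor visual outcome. No adverse-effect rate is given, so 5% is assumed.
- Group sizes: none stated, so all splits below are assumptions.

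**Step 1. One event in a subgroup of k out of N, none in the rest**

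X² = N(N − k) / [k(N − 1)] on 1 df. Two-sided Fisher p = k/N when k < N/2. The expected event count in the subgroup is also k/N.

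| N | k | X² | chi-square p | Fisher p |
|---|---|---|---|---|
| 20 | 4 | 4.21 | 0.040 | 0.20 |
| 30 | 3 | 9.31 | 0.002 | 0.10 |
| 30 | 5 | 30×25/(5×29) = 5.17 | 0.023 | 0.167 |
| 30 | 6 | 4.14 | 0.042 | 0.20 |
| 40 | 8 | 4.10 | 0.043 | 0.20 |
| 98 | 20 | 98×78/(20×97) = 3.94 | 0.047 | 0.204 |

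Significance needs X² ≥ 3.84, which for larger N means (N − k)/k ≥ about 3.84, or k/N ≤ 1/4.84 = 0.21. So one event is declared significant whenever it falls in a subgroup of up to about 20% of the patients: k ≤ 2, 4, 6, 8, 10 and 20 at N = 10, 20, 30, 40, 50 and 98. Given exactly one event placed at random, this happens with probability k/N, up to about 20%. Fisher's test calls one event significant only if k/N ≤ 0.05. The Yates-corrected p for 5 of 30 is 0.36.

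**Step 2. Type I error of the 0.05 rule, 30 children, equal true rates (full enumeration)**

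| Split | 5% rate | 12% rate | 28% rate |
|---|---|---|---|
| 15/15 | 0.5% | 3.2% | 5.5% |
| 24/6 | 9.0% | 6.2% | 4.0% |
| 25/5 | 7.1% | 4.4% | 3.9% |
| 27/3 | 4.1% | 4.0% | 3.5% |
| 16/8/3/3 | 8.8% | 6.3% (6.4% by simulation) | 4.4% |

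Other splits of 30 at 5%: 20/10 gives 3.1%, 22/8 gives 2.1%, 18/12 gives 1.0%. Other sizes at 5%: 16/4 gives 8.7%, 32/8 gives 8.6%, 30/10 gives 2.3%, 78/20 gives 5.0%.

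**Step 3. Pre/post outcomes in the same children**

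One event against none in 30 children gives chi-square p = 0.31, so the single-event problem does not arise here. Pairing is ignored, however. Four new events against none in 30 gives X² = 60×(4×30)²/(30×30×4×56) = 4.29, p = 0.038. The exact McNemar p is 2×0.5⁴ = 0.125.

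**Step 4. Price of Fisher's test**

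Its type I error is 0.7% (25/5) and 1.1% (24/6) at a 5% rate, and 2.2% and 2.4% at 28%. An expected-count trigger of 5 would also apply it at 28%, since 5 × 0.28 = 1.4 and 6 × 0.28 = 1.7.

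**The case against.** The strongest reply is that these between-group tables are not planned. The plan's stated structure is pre versus post. Arthritis type and ANA status are eligibility items, and no test of biologic type against adverse effects is written down. That stands, so the consequence is conditional. It does not remove the gap, because the plan announces significance testing of categorical data and lists biologic type and adverse effects for analysis. Whatever comparison is made falls under the chi-square sentence.

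A second reply is that rare events are assumed. For complications this is right: the plan's own 28–67% is not rare, and at 28% chi-square is close to or below nominal in every split tried. For adverse effects the plan gives no rate either way.

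A third reply is that a p-value conditional on the event landing in the small group is not the error rate of the rule. This also stands. The most striking single-event case, 27/3 with p = 0.002, belongs to a split whose overall error at a 5% rate is 4.1%, below nominal.

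Finally, this is a largely descriptive file review and Fisher's test costs power. Both are fair, and they limit the weight of the point without removing it.

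**Conclusion.** The plan names no method suited to sparse categorical tables, and its stated rule can give a misleading p-value if rare adverse effects are compared between unequal groups. The single-event result depends on the subgroup's share rather than on total size, and holds from 10 to 98 children. The error rates in Step 2 rest on the assumed 30 children, splits and event rates. For 30 children they range from 0.5% to 9.0% at a 5% rate, about 3% to 6% at 12%, and 3.5% to 5.5% at 28%.

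A reader might infer more: that the cohort will be small with few events, that splits by arthritis type or ANA status will be tested, or that one adverse effect would be reported as a significant safety difference. The documents do not support these. They give neither the analysed number nor an adverse-effect rate, and they schedule no such comparison. Nor do the figures support a general claim that chi-square is anti-conservative here, since many splits are at or below 5%. The point is confined to rare events in unbalanced groups. It is worth correcting because the repair is cheap.

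**What to change.** Keep the chi-square sentence in the Statistical analysis plan and add after it:

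> For comparisons between independent groups, Fisher's exact test (Fisher-Freeman-Halton for tables larger than 2x2) will be used when any expected count is below 5. Pre/post binary outcomes in the same children will use the exact McNemar test. Counts and denominators will be shown with every p-value.

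The existing sentence should not simply be replaced by a rule for between-group comparisons, because that would leave the main pre/post comparison with no categorical test at all.

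The cost is three sentences and no new data. The team should confirm that its SPSS 22 installation offers the exact test for larger tables. The statistical price is lost power: Fisher's test is well below its nominal level in these splits, and the expected-count trigger will sometimes apply it where chi-square was adequate. Showing the counts lets readers judge a sparse table for themselves.
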